18.0 Confidentiality

A. Confidentiality of Study Data

Describe the local procedures for maintenance of confidentiality of study data and any records that will be reviewed for data collection.

18.1 A. Where and how will all data and records be stored? Include information about: password protection, encryption, physical controls, authorization of access, and separation of identifiers and data, as applicable. Include physical (e.g. paper) and electronic files.

Response:

Data collected via surveys will be entered directly into a web-based REDCap survey. Only the research team will have access to the survey data

The REDCap database is hosted at the University at Buffalo School of Medicine, Office of Medical Computing. REDCap data projects rely on a thorough study-specific data dictionary defined in an iterative self-documenting process by members of the research team. In terms of regulatory compliance, REDCap can be fully personalized to meet individual project's need for collecting and storing participant data.

. In some cases, if internet access is not available and a paper copy of the survey is needed those copies will be stored in a locked file cabinet. A locked file cabinet in room 814 Kimball Tower, UB South Campus. The room is within the Department of Community Health and Health Behavior. Only the PI and project coordinator will have a key that can access the room and cabinet.

The only personally identifying information from study participants will be their names, addresses, e-mail addresses, and phone numbers so that we can contact them

for follow-up surveys and incentive payment. This data will be stored directly in REDCap. Each subject will receive an identification number which will be used to designate their data. Personal contact information will be stored separately from survey data. Any files linking this information will be password protected and will be permanently deleted as soon as the data collection is completed and payment has been received. Data files prepared for analysis will not include any identifiers.

18.2 A. How long will the data be stored?

Response: Any other paper data collection tools will be destroyed after the data has been analyzed. De-identified electronic data will be retained indefinitely.

18.3 A. Who will have access to the data?

Response: Only the research team members responsible for data collection will have access to identifiable information. All team members will receive appropriate training on maintaining confidentiality and protecting human subject.

18.4 A. Who is responsible for receipt or transmission of the data?

Response: The Principal Investigator and project coordinator are responsible for receipt and transmission of the data.

18.5 A. How will the data be transported?

Response: Electronic and paper survey data collected by UB research team at community sites will be collected via password protected tablets and kept in secure files for transport back to Buffalo to be stored in a locked filing cabinet (Kimball 324). The data will stay in the possession of the UB research team at all times.

B. Confidentiality of Study Specimens

Describe the local procedures for maintenance of confidentiality of study specimens.

N/A: No specimens will be collected or analyzed in this research.
(*Skip to Section 19.0*)

18.6 B. Where and how will all specimens be stored? Include information about: physical controls, authorization of access, and labeling of specimens, as applicable.

Response:

18.7 B. How long will the specimens be stored?

Response:

18.8 B. Who will have access to the specimens?

Response:

18.9 B. Who is responsible for receipt or transmission of the specimens?

Response:

18.10 B. How will the specimens be transported?

Response:

19.0 Provisions to Monitor the Data to Ensure the Safety of Subjects

- N/A: This study is not enrolling subjects, or is limited to records review procedures only. This section does not apply.

NOTE: *Minimal risk studies may be required to monitor subject safety if the research procedures include procedures that present unique risks to subjects that require monitoring. Some examples include: exercising to exertion, or instruments that elicit suicidality or substance abuse behavior. In such cases, N/A is not an acceptable response.*

19.1 *Describe the plan to periodically evaluate the data collected regarding both harms and benefits to determine whether subjects remain safe.*

Response: This is a low risk study. We do not anticipate any harm to the participants. We are confident that the procedures outlined will limit any risk or breach of confidentiality. In the rare event that an adverse event occurs, study staff has the responsibility of reporting it to the PI within 24 hours. In turn, the PI will be responsible for reporting all adverse events in accordance with the policy of the UB IRB. Because of this low risk status, the data safety monitoring plan (DSMP) will focus on close monitoring by the principal investigator (PI) in conjunction with a safety officer, along with prompt reporting of excessive adverse events and any serious adverse events to the NIH and to the IRB at the University at Buffalo.

Because of this study's low risk status, the data safety monitoring plan for this study will focus on close monitoring by the principal PI along with prompt reporting of excessive adverse events and any serious adverse events to the IRB.

19.2 *Describe what data are reviewed, including safety data, untoward events, and efficacy data.*

Response: Recruitment, drop-out, and missing data will be reviewed. Anything affecting statistical power will also be reviewed.

19.3 Describe any safety endpoints.

Response: As we do not anticipate this study having any higher risk than normal participation in exercise we do not have any safety endpoints.

19.4 Describe how the safety information will be collected (e.g., with case report forms, at study visits, by telephone calls with participants).

Response: Safety information will be collected at study visits and telephone calls with participants if necessary.

19.5 Describe the frequency of safety data collection.

Response: Study visits and telephone calls with participants occur at baseline and 12 month follow-up. Participants will be provided contact information for the study project coordinator as well as the Institutional Review Board in the event that they need to report a complaint or concern at any point in the study.

19.6 Describe who will review the safety data.

Response: A safety officer will be appointed who does not have a scientific, financial, or other conflict of interest related to the study and is not a collaborator or association of the principle investigator.

19.7 Describe the frequency or periodicity of review of cumulative safety data.

Response: Data will be reviewed quarterly to assess safety.

19.8 Describe the statistical tests for analyzing the safety data to determine whether harm is occurring.

Response: We do not anticipate this study to be higher risk; therefore, we will not be analyzing safety data.

19.9 Describe any conditions that trigger an immediate suspension of the research.

Response: We do not anticipate this study to be higher risk; therefore, we do not require conditions that will trigger immediate suspension of the study.

20.0 Withdrawal of Subjects

- N/A:** This study is not enrolling subjects. This section does not apply.

20.1 Describe anticipated circumstances under which subjects may be withdrawn from the research without their consent.

Response: In the event [site] withdraws from the study, participants may no longer be able to participate in the study and as a result will not be eligible for future incentives. If this occurs, the Veggie Van Study team will contact participants about the change in their enrollment status.

20.2 Describe any procedures for orderly termination.

NOTE: Examples may include return of study drug, exit interview with clinician. Include whether additional follow up is recommended for safety reasons for physical or emotional health.

Response:

20.3 Describe procedures that will be followed when subjects withdraw from the research, including retention of already collected data, and partial withdrawal from procedures with continued data collection, as applicable.

Response: If a participant decides to leave the study, already collected data may not be removed from the study database unless they request that their data be destroyed.

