4.0 Study Design

4.1 *Describe and explain the study design (e.g. case-control, cross-sectional, ethnographic, experimental, interventional, longitudinal, observational).*

Response: This Veggie Van effectiveness and implementation study, funded by the NIH, will be overseen by Drs. [name], [name], Co-Investigator, [name], Co-Investigator, and [name], Co-Investigator. This study will be coordinated by project coordinators and staff at UB and UNC.

For Aim 2 of the study, all study related procedures will be carried out by UB staff.

Aim 2: After 9 qualified organizations* have been identified among applicants, we will randomize proposed MM sites (33 total across all partner organizations), to an intervention (MM program implementation) or comparison condition (extended planning). Randomization will be stratified within each organization so that each organization will have 2 intervention and 2 comparison sites. One organization will have 5 sites. The 5th site will allow for more thorough testing of protocol procedures. This ensures that study groups will be balanced at the organizational level. The condition for which each proposed MM location was selected will be communicated at the time of award. Organizations will communicate to intervention sites that they want to open a MM at that location within the next year. Organizations will communicate to comparison sites that they want to work with them on a food systems planning process to determine if a MM program is the right fit for their location. At the end of the year-long planning process with comparison sites, the organization and proposed MM site will decide together how to proceed (start a MM, apply for grant funding for a different project; etc.).

Both arms will undergo community engagement efforts that serve to both identify potential research participants and engage them in the planning for a MM. Intervention sites will work with a community advisory committee to develop an engagement plan to raise community awareness of the forthcoming MM. Comparison sites will work with a community advisory committee to engage community members in a food access planning process.

Both intervention and comparison sites will distribute sign-up forms as part of the community engagement process. UB staff will identify from the sign-up forms those interested in participating in the study. Consent will be obtained via phone. Phone surveys and in-person data collection will then be completed.

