Aim 2: In this cluster-randomized study, our primary outcome is change in F&V intake (cups/day) at 12 months using the 24 hour recall, thus, we will compare the difference in mean changes in F&V between intervention and comparison group participants. Our primary analysis will test the hypothesis under the intent-to-treat principle using a Generalized Linear Mixed Model (GLMM) that will account for the correlation induced by the clustering of participants within sites. The GLMM (see below) will include a random intercept for sites (β_0) fixed effects for the baseline value of the primary outcome (β_1) and the intervention (β_2) to test if the differences in mean changes in primary outcomes is zero where β_0 is the fixed intercept and e is error.

$$\text{Change in Primary Outcome}_{9m} = \beta_0 + \beta_1 \text{Primary Outcome}_{baseline} + \beta_2 \text{Intervention} + b_0 + e$$

Including the baseline values score as a covariate in an analysis of covariance (ANCOVA, in our case a GLLM ANCOVA) is known to be a more powerful test than a group comparison of baseline to post-intervention change. In order to further explore the intervention effect, we will fit FLMMs that (1) adjust for baseline covariates of interest; (2) adjust for baseline variables distributed differently between intervention groups; (3) test interaction terms between treatment group and other covariates; and (4) complete sub-group analyses. Specifically, we will look at differences in changes of F&V consumption, perceived access and self-efficacy by intervention usage. Additionally, if we see correlations between changes in F&V consumption, self-efficacy, intervention usage and/or perceived access at 12 months, we will conduct analyses to determine if these changes mediate the intervention effect. In addition, we will expand the regression models by including interaction terms to examine the heterogeneity of intervention and the role of moderators such as organizations or community types.

17.2 If applicable, provide a power analysis.

NOTE: This may not apply to certain types of studies, including chart/records reviews, survey studies, or observational studies. This question is asked to elicit whether the investigator has an adequate sample size to achieve the study objectives and justify a conclusion.

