Infants, and Children (WIC), Temporary Assistance for Needy Families (TANF), Medicaid, Work First, and/or housing assistance.

The intervention is an evidence-based model intended for mobile markets, the Veggie Van model. Informed by the social cognitive theory, the Veggie Van model was designed to address the multiple dimensions of access to fresh produce for lower-income and underserved communities: acceptability, availability, affordability, accessibility, and accommodation. The VV program also includes a cooking and nutrition education component to improve self-efficacy for finding, purchasing, and preparing fruits and vegetables (F&V). Lastly, acceptance of SNAP and participation in local incentive programs further increase affordability.

Data collection will take place at baseline (prior to market launch and planning activities) and approximately 12-month follow-up while the market is still in operation and the planning site has not yet started a market. Data will be collected from market and planning site participants through surveys, 24hr-dietary recalls, and an in-person data collection event (where available). Baseline and 12-month follow-up surveys will include dietary-related psychosocial measures. These surveys will be administered over the phone. The main individual-level outcome, change in F&V intake at 12 months, will be measured through four 24-hour recalls (2 at baseline and 2 at 12 months), which will be administered over the phone by trained interviewers. One recall at each time point will be from a weekday and the other from a weekend day. Recalls will be collected using the Nutrition Data Systems for Research (NDSR) computer-based software application. A participant will receive The Food Amounts Booklet via mail after the baseline survey to have as a visual reference for the 24-hour recalls. In addition to survey data, body mass index (BMI) and dermal carotenoids will be measured at in-person data collection events at baseline and 12 months. Figure 1 illustrates a flowchart of the sequence of study events including partner selection, site randomization, and participant study activities.

Figure 1: Study sequence and data collection events

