(race $p=.01$; income: $p=0.02$). Including the baseline values as a covariate in an analysis of covariance (ANCOVA) is known to be a more powerful test than a group comparison of baseline to post-intervention change (42, 43). ANCOVA is not distorted by regression towards the mean bias, whereas a change analysis is subject to that bias (42, 43). We also conducted a sensitivity analysis excluding extreme F&V reporters, defined as participants who had a change (increase or decrease) greater than 10 servings of F&V per day based on generating histograms and identifying outliers in the data distribution. We conducted additional analyses comparing change in F&V intake for those who reported ever purchasing from VV (VV users) to those who did not report shopping at VV (VV non-users), including delayed-intervention control participants. Due to major disruptions to VV operations in the beginning of the study period (2020), we also looked for differences among a sub-sample of sites that launched after the peak of COVID-19 related closures defined as launching in 2021 or later (i.e., post-covid sites). All secondary outcome analyses were conducted using GLMMs and controlled for baseline covariates of interest and clustering within sites.

Additional analyses by question set can be found below:

Question Set	Answer options	Variable Creation	Analysis Plan
Demographics (13) Weight is asked again at follow-up	various	Will combine categories with small numbers of respondents BMI: created from height and weight	
For all main outcomes we need to control for site and relevant demographic variables
 
 1. Descriptive 2. Will test for differences between Ix and Control groups and include any variables that differ as co-variates in outcome analyses 3. BMI is Aim 1 outcome- compare intervention and control at 6 and 12 months. We expect BMI to stay the same for intervention at 6 months and decrease at 12 months whereas control will increase over time.

NCI F&V Screener (11)*	Frequency (per day, week or month) plus Portion Size	See below for scoring	Aim 1 Outcome. We hypothesize an increase in F&V consumption for intervention compared to control at 6 months.

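### Protocol 20.1 lets participants be withdrawn when their site withdraws, and the SAP ties 12-month follow-up to market status, so whole randomised sites can be lost from an analysis the Protocol calls intent-to-treat

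*Protocol*

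**What the plan says.** - **Protocol 20.1.** The form's prompt is "Describe anticipated circumstances under which subjects may be withdrawn from the research without their consent". The only circumstance given is a site's departure: if it "withdraws from the study, participants may no longer be able to participate in the study and as a result will not be eligible for future" payments. The team then tells participants that their enrolment status has changed.
- **Protocol 20.3.** Retention of data is addressed only for a person's own choice: "If a participant decides to leave the study, already collected data may not be removed from the study database" unless they ask for its destruction. Site withdrawal is not mentioned.
- **SAP 2.** Follow-up is described as "approximately 12-month follow-up while the market is still in operation and the planning site has not yet started a market".
- **Protocol 10.1.** Participants are contacted one year after baseline. Market status is not a condition.
- **Protocol 2.1 and 17.1.** Both name intent-to-treat. Section 17.1 reads: "Our primary analysis will test the hypothesis under the intent-to-treat principle".
- **SAP 5 and 6.** The analysis population repeats the eligibility criteria. The SAP does not use the term intent-to-treat, has no rule for participants of withdrawn sites, and gives no missing-data method.
- **Who collects the outcome.** Protocol 4.1 states: "For Aim 2 of the study, all study related procedures will be carried out by UB staff". The table in 10.1 lets partner staff take in-person measurements but keeps telephone surveys and recalls with the university team.

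**The concern.** The site is the unit of randomisation. The primary outcome is change from baseline to 12 months, so a participant released before the 12-month recalls contributes nothing to the primary model, even if the baseline data are kept. A withdrawn site can therefore disappear from the comparison as a whole cluster.

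The reasons for such a loss may not be neutral. An intervention site has to host a market for at least a year, while a comparison site takes part in planning. A site that leaves because the market was hard to sustain is one that an intent-to-treat analysis needs to keep. A planning site that opens a market early is also informative, and the SAP wording could leave it out.

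The loss is avoidable. The survey and recalls are done by telephone with contact details that the university team holds. Only height, weight and the finger scan depend on access to the site.

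**Working it through.** **1. The plan's own figure.** Inputs from SAP 2.1: SD of change 2.7, ICC 0.08, 21 per site, 12 sites per arm, difference 1 cup/day, one-sided 0.05.

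- Design effect = 1 + (21 − 1) × 0.08 = 2.60
- Variance of a site mean = 2.7² × 2.60 / 21 = 0.903
- SE of the difference = √(0.903 × 2/12) = 0.388
- Power = 0.825 (normal approximation) or 0.803 (noncentral t, 22 df)

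The SAP's 80% reproduces. Protocol 17.2 states at least 90% on the same inputs, which does not reproduce; that is a separate matter. The inputs are usable for illustration.

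**2. If closed sites are lost.** Assumptions not in the documents: 16 sites per arm (half of the SAP's 32), 21 completers per site, a true effect of 1 cup/day where the market runs and 0 at k closed intervention sites, and all losses in that arm.

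- All-sites effect = (16 − k)/16
- Estimate if the k sites are lost = 1.00
- Overstatement = k/16

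One-sided power by noncentral t:

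| k lost of 16 | All-sites effect | Overstatement | Power, all kept | Power, k dropped |
|---|---|---|---|---|
| 1 | 0.94 | 0.06 | 0.86 | 0.89 |
| 2 | 0.88 | 0.12 | 0.82 | 0.88 |
| 3 | 0.81 | 0.19 | 0.76 | 0.86 |
| 4 | 0.75 | 0.25 | 0.70 | 0.85 |

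If the lost sites had half the effect (0.5), the overstatement halves, to between 0.03 and 0.12.

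**3. If lost sites simply have lower change, with no true effect.** Between-site SD = 2.7 × √0.08 = 0.764. If k of 16 sites in one arm are lost and they average one site-SD below the rest of the distribution's centre, that arm's mean rises by k × 0.764/(16 − k): 0.05, 0.11 and 0.25 cups/day for k = 1, 2 and 4.

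**4. Direction.** The formula in step 3 applies to either arm. Two such intervention sites lost moves the difference by +0.11; two such planning sites lost moves it by −0.11; two in each arm cancels. The sign depends on which sites go and why, and the documents do not say.

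**5. Precision.** With 16 against 17 sites (an assumed split of the Protocol's 33), SE = √(0.903 × (1/16 + 1/17)) = 0.331. With 14 against 17 it is 0.343, a rise of 3.6%. Precision is not the main issue.

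**The case against.** Several points on the other side stand.

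- **Withdrawal is not closure.** Section 20.1 concerns a site leaving the study and says participants *may* be unable to continue. It does not mention a market that closes or pauses. A reader might infer that participants of failed markets are removed; no passage orders that.
- **The SAP wording describes timing.** It is not written as an exclusion rule, and it conditions both arms. A reader might infer a contrast of surviving markets against every planning site, biased towards the intervention. The planning-site half of the same sentence contradicts that reading.
- **Protocol 10.1 is unconditional.** If it governs, participants would be called at one year regardless. That leaves the two documents to be reconciled.
- **The 2020 disruption is not evidence of lost sites.** SAP 6 mentions it to explain an additional look at sites launched in 2021 or later, which suggests that earlier sites stayed in the main analysis.
- **Losses may be balanced.** Each organisation has sites in both arms, so an organisation that leaves takes both. The arm-specific risk lies with single sites.
- **Over-recruitment is planned.** Protocol 17.2 and SAP 2.1 recruit 33 or 32 sites against 24 needed. That protects power but does not remove bias from selective loss.
- **It may be late.** The SAP is dated 2/3/2025, is partly in the past tense and quotes baseline p-values, so missed calls may not be recoverable.

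These points limit how strongly the concern can be put. None of them supplies a rule that keeps participants of a withdrawn site in follow-up or in the analysis.

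**Conclusion.** The concern holds as a conflict between written provisions. Section 20.1 permits participants to be withdrawn because their site left, and SAP 2 adds a market-status condition that Protocol 10.1 does not have. Neither is needed to obtain a telephone outcome. Following them can remove whole randomised clusters after randomisation, contrary to the intent-to-treat principle, and the SAP has no analysis set or missing-data rule to correct for it.

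The documents do not show that any site was lost, that closed-market sites are excluded, or that the result favours the intervention. Direction and size are unknown. The range of 0.06 to 0.25 cups/day, against a planned effect of 1 cup/day, rests on assumed values for the number of lost sites, their arm and their response. It shows that a few sites could matter; it does not estimate what happened.

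**What to change.** - **Protocol 20.1.** State that consented participants of a withdrawn site stay enrolled for the 12-month telephone survey and both recalls, with the matching incentives. Only the in-person visit may be lost.
- **SAP 2.** Align with Protocol 10.1: follow-up 12 months after baseline whatever the market status in either arm, with that status recorded.
- **SAP 5 and 6.** Define the primary set as participants of all randomised sites, analysed as assigned. Report site withdrawals and market closures by arm.
- **If follow-up has ended.** The analysis-set and reporting changes still apply. Add a sensitivity analysis for lost sites, for example all-sites effect = [(16 − k) × estimate + k × d]/16 over a stated range of d, the effect assumed at the k lost intervention sites, with the actual site counts and a matching term for lost planning sites.

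**Cost.** From Protocol 25.1, the survey ($15) plus both recalls ($15) is $30 per retained participant. It is $45 for Phase 2 participants recruited after the in-person event, whose two recalls are paid separately (3 × $15). For a site of 30 that is $900 to $1,350 if all are reached, and these payments are already in the planned schedule. Staff calls are extra work, and the estimated effect may be smaller.
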